### Follow-up of AEs and SAEs

---

- The investigator is obligated to perform or arrange for the conduct of supplemental measurements and/or evaluations as medically indicated or as requested by the Sponsor to elucidate the nature and/or causality of the AE or SAE as fully as possible. This may include additional laboratory tests or investigations, histopathological examinations, or consultation with other health care professionals.
- New or updated information will be recorded in the originally completed CRF.
- The investigator will submit any updated SAE data to the Sponsor within 24 hours of receipt of the information.

---

### 10.3.4 Reporting of SAEs

---

#### SAE Reporting to the Sponsor via an Electronic Data Collection Tool

---

- The primary mechanism for reporting an SAE will be the electronic data collection tool.
- If the electronic system is unavailable, then the site will use the paper SAE data transmission (see next section) in order to report the event within 24 hours.
- The site will enter the SAE data into the electronic system as soon as it becomes available.
- After the study is completed at a given site, the electronic data collection tool will be taken off-line to prevent the entry of new data or changes to existing data.
- If a site receives a report of a new SAE from a study participant or receives updated data on a previously reported SAE after the electronic data collection tool has been taken off-line, then the site can report this information on a paper SAE form (see next section) or to the Sponsor's Medical Monitor by telephone.
- Contacts for SAE reporting can be found in the investigator Site File.

---

---

**SAE Reporting to the Sponsor via Paper CRF**

---

- Email transmission of the SAE paper CRF is the preferred method to transmit this information to the Sponsor's Medical Monitor.
- In rare circumstances and if email transmission is not feasible, notification by telephone is acceptable with a copy of the SAE data collection tool sent by overnight mail or courier service.
- Initial notification via telephone does not replace the need for the investigator to complete and sign the SAE CRF pages within the designated reporting time frames.
- Contacts for SAE reporting can be found in the investigator Site File.

---

**10.4 Appendix 4: Visit Description****10.4.1 Visit 1 – Screening (Approximately 2 to 8 Weeks)**

Screening may take place over multiple site visits. At the Screening Visit, the following procedures and assessments will be performed:

- Obtain signed informed consent from participants  
Note: No screening procedures should be performed unless written informed consent has been obtained
- Allocation of a unique participant number
- Review of eligibility requirements; no participant should receive study intervention unless all inclusion and exclusion criteria are met listed in Section 5.1 and 5.2.  
Confirmation of selection criteria may be based on medical records for some conditions, but laboratory test results must be available for the listed items to confirm eligibility.
- Collect demographic data (age, sex [male only], race, ethnicity, and gene defect)
- Full physical examination including neurological standard assessment, height, and weight
- Collect information on activity level (type of sports, hrs/wk)
- Obtain a complete medical and surgical history (general, disease, family history of hemophilia, and history of inhibitor development)
  - Include any information on cardiovascular risk, hepatic disease, renal impairment, prior use of PEGylated medications (e.g., PEG- interferon, PEG-anti- tumor necrosis factor [TNF])
  - Specific information on history of hemophilia (date of diagnosis, start of therapy, prior and current factor VIII products, number of ED, type of factor VIII gene

mutation (from history), family history, FVIII level, family and personal history of past inhibitor formation, current treatment product and regimen, number and type of bleeds in the last 12 months, and presence and location of target joints.) If available, data on prior PK with the participants' previous FVIII product will be collected (e.g. recovery and half-life).

- Collect information on previous medication (medication history)
- Vital signs (Heart rate, respiratory rate, and blood pressure; see Section 8.2.3)
- Urine sample (routine urinalysis and renal biomarkers; see Table 10-1)
- Blood samples for (see details in Table 10-1):
  - Laboratory evaluation (hematology and clinical chemistry)
  - HIV screening (in case negative result in patient documentation is older than 1 year at date of screening)
  - CD 4+ cell count (only if participant is HIV positive)
  - Immunogenicity testing
  - PEG level in plasma
- Training on and dispense of EPD devices
- Training and dispense of activity tracker; ask the participant to wear activity tracker for continuous 2-3 weeks after screening before Baseline Visit (see Section 8.1.3)
- Concomitant medication review
- AE review

#### 10.4.2 Visit 2 – Baseline Predose (Day 1)

This visit will be serving as the Baseline Visit; it will include the first administration of study intervention. The Baseline Visit should take place within 2 to 8 weeks after Screening Visit and at least 72 hour after last FVIII product administration.

This visit should start with the following assessments:

- Confirmation of eligibility including check of laboratory test results  
Note: Participants must have negative results from the central laboratory for inhibitory antibodies against FVIII (< 0.6 BU determined with the Nijmegen modified Bethesda assay)

Thereafter, the following procedures and assessments will be performed and data recorded:

- Remind the participants to wear the activity tracker for 2-3 continuous weeks after the start of treatment before Visit 3
- Concomitant medication review
- AE review
- Vital signs (Heart rate, respiratory rate, and blood pressure; see Section 8.2.3)

- Urine sample (routine urinalysis and renal biomarkers; see [Table 10-1](#))
- Blood sample collection **before** administration of study intervention
  - Blood samples for:
    - Immunogenicity testing
    - Incremental recovery of Jivi
- In-hospital injection of Jivi
- Procedures and sample collection **after** administration of study intervention
  - Blood samples for:
    - Incremental recovery of Jivi (15-30 min after end of injection; see Section [8.1.2](#))
  - In case of any injection related AE at site, vital signs will be collected
- Dispense study intervention for home injections in accordance with IxRS drug dispensing schedule
- Instruction on the treatment regimen to be administered to the participant
- Check of EPD entries and bleeding history
- Begin regular monthly contact between participant and the site to check EPD documentation and AE review until the End of Study/Early Termination

#### 10.4.3 Visit 3 – ED 10-15 (Week 8-10)

This visit should take place at least 72 hours after the last injection of Jivi.

- Dose regimen adjustment
- Blood sample collection **before** administration of study intervention:
  - Immunogenicity testing
  - Incremental recovery of Jivi
- In-hospital injection of Jivi
- Procedures and blood sample collection **after** administration of study intervention
  - Incremental recovery of Jivi (15-30 min after end of injection; see Section [8.1.2](#))
  - In case of any injection related AE at site, vital signs will be measured
- Concomitant medication review
- AE review
- Check of EPD entries and bleeding history
- Dispense study intervention for home injections in accordance with IxRS drug dispensing schedule

- Return used and unused study intervention
- Continue regular monthly contact between participant and the site to check EPD documentation and AE review until the End of Study/Early Termination

#### **10.4.4 Visit 4 – ED 50-75 (Month 6 ± 14 days)**

This visit should take place approximately 48 or 72 hours (if not possible then 96 hours) after the last injection of Jivi.

- Ask the participant to wear activity tracker for continuous 2-3 weeks after Visit 4 (Month 6) before Visit 5 (Month 12)
- Body weight measurement
- Concomitant medication review
- AE review
- Blood samples for (see details in [Table 10-1](#)):
  - Immunogenicity testing
  - FVIII level
- Dispense study intervention for home injections in accordance with IxRS drug dispensing schedule
- Return used and unused study intervention
- Check of EPD entries and bleeding history
- Continue regular monthly contact between participant and the site to check EPD documentation and AE review until the End of Study/Early Termination

#### **10.4.5 Visit 5 – ED 50-75 (Month 12 ± 14 days)**

This visit should take place approximately 48 or 72 hours (if not possible then 96 hours) after the last injection of Jivi.

- Body weight measurement
- Concomitant medication review
- AE review
- Urine sample (routine urinalysis and renal biomarkers; see [Table 10-1](#))
- Blood samples for (see details in [Table 10-1](#)):
  - Laboratory evaluation (hematology and clinical chemistry)
  - Immunogenicity testing
  - FVIII level

- Dispense study intervention for home injections in accordance with IxRS drug dispensing schedule
- Return used and unused study intervention
- Check of EPD entries and bleeding history
- Documentation of activity tracker; return activity tracker
- Continue regular monthly contact between participant and the site to check EPD documentation and AE review until the End of Study/Early Termination

#### **10.4.6 Visit 6 if needed – ED 50-75 (Month 18 ± 14 days)**

- Body weight measurement
- Concomitant medication review
- AE review
- Dispense study intervention for home injections in accordance with IxRS drug dispensing schedule
- Return used and unused study intervention
- Check of EPD entries and bleeding history
- Continue regular monthly contact between participant and the site to check EPD documentation and AE review until the End of Study/Early Termination

#### **10.4.7 Last Visit – ED 100 (End of Study/Early Termination + 14 days)**

This visit should take place at least 72 hours after the previous injection of Jivi.

The following procedures and assessments will be performed in participants reach ED 100 or at the time of premature termination:

- Concomitant medication review
- AE review
- Full physical examination including neurological standard assessment, height, and weight
- Vital signs (Heart rate, respiratory rate, and blood pressure; see Section 8.2.3)
- Urine sample (routine urinalysis and renal biomarkers; see [Table 10-1](#))
- Laboratory evaluation (hematology and clinical chemistry)
- PEG level in plasma
- Blood sample collection **before** administration of study intervention
  - Immunogenicity testing

- Incremental recovery of Jivi
- In-hospital injection of Jivi
- Procedures and blood sample collection **after** administration of study intervention
  - Incremental recovery of Jivi (15-30 min after end of injection; see Section [8.1.2](#))
  - In case of any injection related AE at site, vital signs will be measured
- Return used and unused study intervention
- Check of EPD entries and bleeding history and return EPD
- Return activity tracker in case of early termination before Visit 5

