**Table 1-1 Study Schedule of Activities (SoA)**

Procedures	Screening a	Baseline Pre-dose	ED 10-15	ED 50-75 Every 6 months			End of study 100 ED / Early Termination
	Visit 1 2-8 Wks before baseline	Visit 2 Day 1	Visit 3 Wk 8-10 b	Visit 4 Month 6 (±14 days) c	Visit 5 Month 12 (±14 days) c	Visit 6 Month 18 if needed (±14 days) c	Last Visit (+14 days)
Recovery (pre and 15-30 min post injection FVIII levels) h		X	X				X
FVIII level after 48 or 72 hours after last injection				X	X		
In-hospital injection of Jivi		X	X				X
AE review	X	X	X	X	X	X	X
Return used and unused study intervention			X	X	X	X	X
Dispense study intervention for home injections			←==continuously in accordance with IxRS drug dispensing schedule==→				
Injection of Jivi			←=====continuously in accordance with assigned treatment regimen=====→				
Concomitant medication review	X		←=====continuously=====continuously=====→				
Patient diary (EPD) documentation	X		←=====continuously=====continuously=====→				
Interaction between participants and investigators			←=====Monthly contact=====→				

Abbreviations: ADA=anti-drug antibody, AE=adverse event, ALT=alanine aminotransferase, AST=aspartate aminotransferase, ED=exposure days, EPD=electronic patient diary, HIV=human immunodeficiency virus, hrs=hours, IxRS=Interactive voice/web response system, max=maximum, and Wk=week.

- The time interval between Screening and Baseline visit is 2 to 8 weeks.
- Although the allowable visit window is ±14 days, visits must occur within the specified ED range.
- Visits should be scheduled within the visit window so that at least one visit occurs in the 50 – 75 ED range.
- HIV screening will be performed only in case that negative result in patient documentation is older than 1 year at date of screening.
- Only in case of Early Termination Visit before V6.
- In case of any injection related AE, vital signs will be collected in addition post-injection for participants.
- At Baseline, Visit 3 and End of Study/Early Termination Visit, blood samples for immunogenicity will be collected before the in-hospital injection of Jivi.
- Recovery should be measured at least 72 h after last injection of FVIII of Jivi.

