## 2.3 Benefit/Risk Assessment

Jivi has received marketing authorization by the FDA, EMA, PMDA, and Health Canada for the treatment and prevention of bleeds in patients  $\geq 12$  years of age.

Jivi has demonstrated the potential for dosing every 5 days or every 7 days in a majority of participants in clinical studies, offering the option of a prophylaxis treatment with less frequent dosing for hemophilia A patients  $\geq 12$  years of age. For the patients with increased bleeding tendency, 2x/week treatment with Jivi provided an efficacious treatment option.

As is the case for all FVIII replacement treatments, the most serious expected adverse event (AE) is the development of inhibitory antibodies against FVIII. No new or confirmed inhibitors have been observed during the clinical studies.

Hypersensitivity reactions are a known and listed adverse event for FVIII products and have been reported with use of Jivi. A clinical immune response associated with anti-PEG antibodies, manifested as symptoms of acute hypersensitivity and/or loss of drug effect has been observed within the first 4 exposure days primarily in children  $< 6$  years of age (Study #15912 PROTECT Kids). CC1 [REDACTED] in

such cases Jivi should be discontinued and patients switched to a previously effective factor VIII product.

Based on available data and considering the medical need, the benefit risk assessment was considered to be positive by Regulatory Authorities.

More detailed information about the known risks and reasonably expected adverse events of Jivi may be found in the SmPC/ Package Leaflet.

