## **7.2      Participant Discontinuation/Withdrawal from the Study**

A participant who withdraws is one who discontinues from a clinical study for any reason. The participant will not suffer any disadvantage as a result.

- A participant may withdraw from the study at any time at his own request without giving reasons, or may be withdrawn at any time at the discretion of the investigator for safety, behavioral, compliance, or administrative reasons..
- At the time of discontinuing from the study, if possible, an early discontinuation/final visit should be conducted, as shown in the SoA. See SoA for data to be collected at the time of study discontinuation and follow-up and for any further evaluations that need to be completed.
- The participant will be permanently discontinued both from the study intervention and from the study at that time.
- If the participant withdraws consent for disclosure of future information, the sponsor may retain and continue to use any data collected before such a withdrawal of consent.
- A participant must be withdrawn from the study if the development of an inhibitory antibody to Jivi that neutralizes activity sufficiently to interfere with effective treatment or requires use of a bypassing agent to treat bleeds.
- A participant must be withdrawn from the study if he fails to comply with scheduled appointments for the study-related evaluations and with EPD data entry to an extent that compromises collection of critical data.
- A participant must be withdrawn from the study if significant concurrent illness or deterioration occurs in the participant's condition, including laboratory values that the investigator deems to be incompatible with the participant's continued safe participation in the study.

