## 8. Study Assessments and Procedures

- Study procedures and their timing are summarized in the SoA and visit description Section 10.4. Protocol waivers or exemptions are not allowed.
- Immediate safety concerns should be discussed with the sponsor immediately upon occurrence or awareness to determine if the participant should continue or discontinue study intervention.
- Adherence to the study design requirements, including those specified in the SoA, is essential and required for study conduct.
- All screening evaluations must be completed and reviewed to confirm that potential participants meet all eligibility criteria.
- Procedures conducted as part of the participant's routine clinical management (e.g., blood count) and obtained before signing of the ICF may be utilized for screening or baseline purposes provided the procedures met the protocol-specified criteria and were performed within the time frame defined in the SoA.
- If deemed necessary for an individual participant, the investigator or designee, at his/her discretion, may arrange visits in addition to the scheduled study visits. Unscheduled visits will be documented in the eCRF.

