**8.1.2 Incremental Recovery of Jivi**

Blood samples for Jivi trough (predose) and recovery levels (15-30 min post injection) will be collected in all participants. Incremental recovery will be determined by collecting a sample for FVIII level before the scheduled injection, and a second sample collected 15-30 min after end of the injection. The exact sampling times before and after injection and the dose administered will be documented in the CRF. Incremental recovery of Jivi is determined by measuring FVIII activity.

Injections given at study visits will be recorded in the site participant records, which will be the source documents and will be used to enter this information in the CRF.

The samples will be collected as described in detail in the laboratory manual. All samples will be processed in the central laboratory. Plasma concentrations of FVIII will be measured using a validated FVIII activity assay ("chromogenic assay").

Samples for incremental recovery should be collected on days when the next prophylactic injection is scheduled and at least 72 h after the prior injection has been given. The measurements should only be performed when the participant is not actively bleeding.

Recoveries should be performed using the participants assigned treatment dose, rounded to full vial size.

Samples will be collected at Baseline, Visit 3 (Week 8-10), and Last Visit, or in case of suspicion of loss of efficacy (LoE)/hypersensitivity and at additional time points based on the investigator's discretion.

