### **Loss of Efficacy (LoE)/Hypersensitivity reaction**

In case loss of efficacy is suspected by the investigator (ie, measured by low FVIII levels, poor recovery, and unexpected clinical symptoms of bleeding or no response to treatment of a bleed) or the participant presents symptoms of an hypersensitivity reaction, plasma samples will be tested for FVIII inhibitor and ADA, and positive screened samples will be further characterized for specificity of the antibody response against Jivi and/or against PEG. Samples that confirmed positive against Jivi will be further analyzed in a modified Nijmegen Bethesda assay for inhibitory activity against Jivi.

In addition to this, incremental recovery following administration of Jivi will be measured. Samples for Jivi trough and recovery levels following an injection of Jivi will be collected when loss of efficacy is suspected (See Section 8.1.2). In case of a slightly reduced recovery (compared to previous product or below 1.5 IU/dl per IU/kg), the recovery should be repeated locally after the next injection.

A clinical immune response manifested as symptoms of acute hypersensitivity and/or loss of drug effect has been observed primarily in children  $< 6$  years, within the first 4 exposure days, which was associated with anti-PEG antibodies. CC1

in such cases Jivi should be discontinued, participants should switch to a previously effective factor VIII product, and the recovery should be measured locally after injection of the previous FVIII which will be normal in these cases, ruling out an inhibitor.

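### Minor: the exit visit lists a Jivi injection with no visible exception for participants already off Jivi; the SAP washout flag cannot test Baseline, and the TEAE window outlasts AE collection

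*Protocol*

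**What the plan says.** **(a) Exit visit.** Protocol 10.4.7 applies one list to completers and early leavers: "The following procedures and assessments will be performed in participants reach ED 100 or at the time of premature termination". The list contains an in-hospital injection of Jivi and a recovery sample after it. The SoA marks the same items in the End of Study/Early Termination column, and footnote g fixes the order: "At Baseline, Visit 3 and End of Study/Early Termination Visit, blood samples for immunogenicity will be collected before the in-hospital injection of Jivi". Section 8 adds: "Adherence to the study design requirements, including those specified in the SoA, is essential and required for study conduct".

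Other sections deal with participants who have stopped Jivi:
- Section 7.1 withdraws anyone who stops Jivi because of an inhibitor and refers to the SoA for the data due at that point.
- Section 7.2 has two relevant bullets: "At the time of discontinuing from the study, if possible, an early discontinuation/final visit should be conducted, as shown in the SoA", and directly after it "The participant will be permanently discontinued both from the study intervention and from the study at that time".
- Section 8.2.1, on loss of efficacy and hypersensitivity, says "in such cases Jivi should be discontinued, participants should switch to a previously effective factor VIII product". Section 2.3 says much the same. The words leading into both are redacted.
- Section 8.1.2 on recovery: "Samples for incremental recovery should be collected on days when the next prophylactic injection is scheduled".

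**(b) Recovery flag.** SAP 4.5 makes a recovery invalid if less than 72 hours have passed since the previous infusion of study drug, and describes this as a check on the washout set by the protocol. Protocol 10.4.2 sets the Baseline washout as 72 hours from the last FVIII product of any kind, and Baseline is where the first study dose is given.

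**(c) Adverse events.** Protocol 9.4.2 and SAP 6.4 count an event as treatment-emergent up to 7 days after the last Jivi injection. Protocol 8.3.1 collects events only to the end of the final visit. After that, only SAEs that the investigator happens to learn of and considers related must be notified.

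**The concern.** On (a), a site that follows the SoA literally and a site that follows the discontinuation text could handle the same participant differently at exit. The difference is whether Jivi is given to someone already taken off it, which bears on participant safety. The study has no data monitoring committee to settle the question.

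On (b), the flag decides which pre-infusion, post-infusion and recovery values enter the summary tables. A check that names the protocol washout but has nothing to measure from at Baseline would let a short washout through unnoticed.

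On (c), TEAEs are a named secondary endpoint, and their window includes days on which nobody is asked about new events. An injection at the last visit makes that stretch as long as it can be.

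**Working it through.** **(a) Passages side by side; no arithmetic applies.**
1. Who is sent to the visit? Everyone who ends early, including inhibitor withdrawals under Section 7.1, which points to the SoA without setting the injection aside.
2. Is the injection conditional? Not in the visible text. The authors did write early-termination conditions elsewhere: return of the activity tracker is conditional in 10.4.7 and in SoA footnote e. The only visible clinical limit on recovery sampling is active bleeding (8.1.2).
3. Does other text point away from an injection? Section 8.1.2 assumes a scheduled prophylactic dose, which a participant already off Jivi does not have. Section 8.2.1 stops Jivi in the cases it describes.
4. Do the planned recovery summaries depend on the answer? Hardly, for participants with a positive inhibitor or anti-drug antibody: SAP 4.5 leaves them out of the recovery analyses and only lists their results.

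The recovery test done to diagnose suspected loss of efficacy or hypersensitivity (8.1.2, 8.2.1) is a separate matter and is not questioned here.

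**(b) Reach and size of the flag gap.**
- Planned recoveries are at Baseline, Visit 3 and Last Visit (8.1.2), for 25-30 participants (Synopsis): 3 × 25 = 75 to 3 × 30 = 90.
- Baseline recoveries, where no earlier study drug infusion exists: 25-30, or one third.
- Assumptions, not in the documents: a residual level R of 5-20 IU/dL in a participant who breaks the washout, a half-life h of 8-18 hours for the earlier product, and t = 0.5-1 hour between the two samples. Dose per kg is 40-60 IU/kg (Protocol 6.1).
- Shift in the mean pre-infusion level per such participant = R/n: 5/30 = 0.17 to 20/25 = 0.80 IU/dL.
- Shift in that participant's own recovery = R × (1 − 2^(−t/h)) / dose. Smallest: 5 × 0.0191 / 60 = 0.0016. Largest: 20 × 0.0830 / 40 = 0.0415 IU/dL per IU/kg.
- Against the 1.5 threshold in Section 8.2.1: 0.0016/1.5 = 0.1% to 0.0415/1.5 = 2.8%. Recovery hardly moves because the pre-infusion level is subtracted.

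The flag also misses other FVIII given around elective major surgery (Protocol 7.1.1).

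**(c) Length of the uncollected stretch.**
- Injected at the Last Visit: 7 − 0 = 7 days.
- Not injected there, with the previous injection at least 72 hours earlier (10.4.7): at most 7 − 3 = 4 days.
- If 25-30 participants are injected: 25 × 7 = 175 to 30 × 7 = 210 participant-days.
- Share of one participant's TEAE window = 7 / (d + 7). For completers d = 99 × dosing interval, taking the 100th exposure day at the Last Visit, one regimen throughout and no extra doses for bleeds:

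| Case | d (days) | Share |
|---|---|---|
| 2x/week | 99 × 3.5 = 346.5 | 7/353.5 = 2.0% |
| every 5 days | 99 × 5 = 495 | 7/502 = 1.4% |
| every 7 days | 99 × 7 = 693 | 7/700 = 1.0% |
| sponsor close-out at 6 months | 182.6 | 7/189.6 = 3.7% |

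Illustration of a very early exit: four doses at 5-day intervals (days 0 to 15) and an exit injection on day 18 give 7/25 = 28%.

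**The case against.** **On (a)** the other side has real weight. Treatment decisions are left to clinical judgment (6.1), urgent safety concerns go to the sponsor (Section 8), the exit visit is held only where possible, and Sections 7.1 and 7.2 cite the SoA for data collection, not for treatment. A reader might infer more than the text supports, in two ways:
- That 7.2 flatly contradicts 10.4.7, so that the protocol orders withdrawn participants to be dosed again. The statement on permanent discontinuation follows the bullet that sends the participant to the final visit, so it can be read as taking effect when that visit ends. It is ambiguous, not contradictory. The sharper tension is between 7.1 and 8.2.1 on one side and the unconditional injection in 10.4.7 and the SoA on the other. Text is also redacted in 2.3, 8.2.1 and 8.3.7, just where an exception could stand.
- That 30 − 25 = 5 participants are affected. At least 25 completers is an expectation, not a limit on dropout, and surplus participants closed out by the sponsor after 6 months (SAP 3) would still be on Jivi.

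**On (b)**, the washout is already required at Baseline, so the gap matters only when a site breaks that rule, and deviations are reviewed under SAP 4.6. This limits the size of the problem. It does not make the flag do what it says.

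**On (c)**, a classification window need not equal the collection period, and TEAEs are reported as incidence, so participant-days enter no planned estimate. Both points are fair. What remains is that events on those days would count as treatment-emergent but are not asked for.

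**Conclusion.** The point holds and is minor overall.

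- **(a)** The visible text gives no single instruction for the exit visit of a participant already off Jivi. How many are affected is unknown and may be zero; the documents give no adult rate of hypersensitivity or loss of effect, and none is assumed. The conclusion depends on the redacted text not already holding the rule.
- **(b)** This one is wrong as written: the flag cannot test the washout it names at one third of planned recoveries. The effect is confined to participants who break the washout and falls mainly on the descriptive FVIII level summaries, at 0.2-0.8 IU/dL on the mean per such participant under the assumed residuals. For recovery itself it is negligible.
- **(c)** Up to 7 days go without active collection after an exit injection, about 1-2% of a completer's window and more for early leavers.

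A reader might also infer that the inhibitor endpoint is compromised by the exit injection. It is not: immunogenicity samples are drawn before it.

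**What to change.** **(a)** Reconcile the SoA column, footnote g and Section 10.4.7 with Sections 2.3, 7.1, 7.2, 8.1.2 and 8.2.1, so that one instruction applies at the exit visit to participants already taken off Jivi. If the redacted text already holds the rule, a cross-reference in the SoA and 10.4.7 is enough. Which clinical rule is right is for the sponsor and is not proposed here. Cost: wording only.

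**(b)** In SAP 4.5, base the validity flag on time since any FVIII product. Other FVIII products are already recorded in the CRF (Protocol 6.5) and the diary (8.1.1); where only a date exists, specify a calendar-day rule in advance. Clarify SoA footnote h, whose wording leaves open whether it means any FVIII product or Jivi alone. Cost: one SAP line and one footnote, with no new data.

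**(c)** Align Section 8.3.1 with the TEAE window through one short contact 7 days after the last injection. Cost: up to 30 contacts and up to 7 days' later end of participation. Failing that, state the limitation in the report. Capping the TEAE window at end of study, as SAP 4.5 does for the bleeding-rate period, is not a remedy: it recovers no uncollected event and would drop related SAEs notified after the visit.
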